**INDICATIONS:**

The Instructions for Use (IFU) for each individual product can be found at <http://www.wright.com/prescribing-use-3>.

**CLINICAL INVESTIGATION DESIGN:**

- Post-Market,
- Multicenter,
- Prospective,
- Non-Randomized

[figure not shown]
[figure not shown]

## 1. Administrative Information

### 1.1. LIST OF ABBREVIATIONS

Acronym	Definition
ADE	Adverse Device Event
AE	Adverse Event
CI	Confidence Interval
CIP	Clinical Investigation Plan
CRF	Case Report Form
eCRF	Electronic Case Report Form
EC	Ethics Committee
EDC	Electronic Data Capture
EQ-5D	A standardized health-related quality of life instrument by the EuroQuol Group
EU MDR	European Medical Device Regulation
FAAM	Foot and Ankle Ability Measure
FR	Final Report
FU	Follow-Up
ICF	Informed Consent Form
ICH-GCP	International Conference of Harmonisation Good Clinical Practice
IFU	Instructions for Use
ITT	Intent-to-Treat
Intra-Op	Intra-Operative
IR	Interim/Annual Report
IRB	Institutional Review Board
LTFU	Lost to Follow-Up
Op	Operative
PP	Per Protocol
Post-op	Post-Operative
Pre-Op	Pre-Operative
SADE	Serious Adverse Device Effect
SAE	Serious Adverse Event
SAP	Statistical Analysis Plan
UADE	Unanticipated Adverse Device Effect

### 1.2. STATISTICAL ANALYSIS PLAN REVISION HISTORY

Version	Effective Date	Description	Reason
1	12 January 2022	Initial Version	n/a

## 2. Introduction

### 2.1. BACKGROUND AND RATIONALE

The European Union (EU) Medical Device Regulation (MDR) 2017/83/EC applies to all medical device manufactures who intend to market their products in the EU. The EU MDR has increased the requirements for clinical data needed for products to maintain certification. Under the regulation, the manufacture must proactively collect and evaluate clinical data to establish and verify:

that under normal conditions of use, a device achieves the performance intended as specified by the manufacturer;

- the clinical benefits of a device as specified by the manufacturer;
- the clinical safety of the device;
  - Identify previously unknown side-effects;
  - Monitor the intended side-effects and contraindications;
  - Identify and analyze emerging risks on the basis of factual evidence;
- ensure the continued acceptability of the benefit / risk ratio; and
- systemic misuse or off-label use with a view to verify the intended purpose is correct.

Wright Medical is conducting this observational study to meet the clinical data requirements for the EU MDR.

The purpose of this post-market clinical observational study is to demonstrate the safety and performance of the Wright product after implantation over a standard follow-up period using patient reported outcome measures (PROMs) related to quality of life and functional improvements, safety of the implants, as well as radiographic assessments (X-Rays).

The outcome measures collected in this study will be analyzed and reported as required for local, regional, and country requirements (i.e., regulatory authorities and notified bodies).

### 2.2. CLINICAL INVESTIGATION DESIGN

This investigation is a global, multi-center, post-market observational study. The study planned to enroll 40 patients per device according to sample size calculations based on the EQ-5D (See study protocol). The enrollment period is expected to be 5 years. Based on the varied definitions of clinical lifetime for each device, the follow-up (FU) period will range 12 weeks to 10 years.

Data will be collected at baseline, surgery, at last scheduled standard of care and/or surgeon release FU time point. Additionally, PROMs and safety may be followed yearly to sufficiently assess the safety of the product over the clinical lifetime as needed based on the current risk analysis for the product.

### 3. Statistical Procedure

#### 3.1. FRAMEWORK

The purpose of this statistical analysis plan is to guide the analysis and production of statistical output for the Wright Foot & Ankle Post-Market Observational Study. The company decided to discontinue enrollment to the study on November 1, 2021. At study end date, there were 122 patients enrolled in the study. The sample size of 40 patients per device that was originally planned in the study was therefore not met.

The study required at least 40 sample size for each Wright medical device (See INT19-MDR-001 Protocol, Version 3). For the same sample size parameters in the protocol  $n=10$ , will yield a power of 0.5. Thus, for the purpose of reporting statistically valid outcomes, descriptive summary statistics will be presented for Wright devices implanted in at least 10 patients enrolled in the study. Patient data on devices that has less than 10 implanted patients will be provided in the listings to be made available for future study or reference. Appendix Table 1 lists the Wright devices that are included in the study.

As the goal of the study is to determine the performance and safety of each device under investigation, analysis of outcomes will be done for each device the patient received. Note that a patient may have received more than one of the Wright devices. In all analysis of outcomes, patient level data will be included in the analysis for each device he/she received.

All analysis to be conducted are of descriptive nature only. No test of hypothesis will be performed. All quantitative variables, including those based on calculations (i.e., improvement from baseline), will be analyzed with a case summary evaluation before the detailed characteristics and parameter can be evaluated. A case summary contains a listing of the number of valid cases/values, missing cases/values (if any) and total cases/values in the specific analysis. The mean and median will be reported to assess the average or centrality of quantitative variables. Improvement from baseline in patient reported outcome (PROM) will be assessed at each post-surgery visit. Improvement will be based on the difference in raw scores.

Whenever the available data allows, the standard deviation, interquartile range (IQR) and maximum and minimum will be calculated. All quantitative variables will be assessed for normality via the Shapiro-Wilk test. The 95% confidence interval (CI) of the mean will be presented when the normality of the data is met.

All qualitative variables, including those based on summaries (secondary elements), will be analyzed listing the proportions, frequencies, column and row totals and missing proportion (if any).

The proportion of device surviving at each visit will be summarized for each device. Rates will be computed based on available data. Missing data will not be imputed.

No imputations for missing data will be conducted.

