**6.2.6 Number of Subjects required to be included in the CI**

We will prospectively collect EQ-5D-5L for subjects enrolled in this study. Because the devices are utilized in a variety of skeletal anatomic locations within the foot and ankle, a literature search was conducted to better understand the EQ-5D outcomes for various orthopedic procedures. Hasson et al. (Hasson et al. Spine. 33(25): 2819-2830, 2008) reported on EQ-5D outcomes from various procedures, including arthrodesis of the ankle or subtalar joints. The sample size calculation is based on precision of estimate from the post-operative EQ-5D:  $0.549 \pm 0.313$  (mean  $\pm$  SD). Using the standard deviation (0.313), a sample size was calculated:

|            |                              |                            |        |      |
|------------|------------------------------|----------------------------|--------|------|
| Alpha=0.05 | Half width (precision) = 0.1 | Standard deviation = 0.313 | Side=2 | n=38 |
|------------|------------------------------|----------------------------|--------|------|

Based on this calculation, a minimum sample size for each device: n = 40 or until sufficient data is collected to satisfy the notified bodies.

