## **7.0 Statistical Considerations**

### **7.1 Study design**

This study is a global, multi-center, post-market observational study to demonstrate the safety and performance of the Wright products listed in Section 3.3. Data will be collected at baseline, surgery, at the last scheduled standard of care and/or surgeon release follow-up (FU) time point. The subjects improvement in post-surgical quality of life will be assessed using EQ-5D-5L and Foot and Ankle Ability Measure (FAAM).

An adverse event resulting from the presence or performance of the device and removal due to implant failure will determine the survivorship of the Wright product. Further, safety will be assessed by subject experience of device complication and adverse events during the study period.

All effectiveness and safety analysis will be performed separately for each Wright Medical device included in the study.

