### **7.2 Sample Size**

We will prospectively collect EQ-5D-5L for subjects enrolled in this study. Because the devices are utilized in a variety of skeletal anatomic locations within the foot and ankle, a literature search was conducted to better understand the EQ-5D outcomes for various orthopedic procedures. Hasson et al. (Hasson et al. Spine. 33(25): 2819-2830, 2008) reported on EQ-5D outcomes from various procedures, including arthrodesis of the ankle or subtalar joints. The sample size calculation is based on precision of estimate from the post-operative EQ-5D:  $0.549 \pm 0.313$  (mean  $\pm$  SD). Using the standard deviation (0.313), a sample size was calculated:

|              |                              |                            |          |        |
|--------------|------------------------------|----------------------------|----------|--------|
| Alpha = 0.05 | Half width (precision) = 0.1 | Standard deviation = 0.313 | Side = 2 | n = 38 |
|--------------|------------------------------|----------------------------|----------|--------|

Based on this calculation, a minimum sample size for each device: n = 40 or until sufficient data is collected to satisfy the notified bodies.

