### 3.1.1. Primary Analysis / Endpoint

Improvements in subject quality of life after surgery will be assessed by constructing 95% confidence interval for the mean change from baseline score in EQ-5D-5L.

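### SAP 3.1 justifies its 10-patient reporting threshold by a power of 0.5 that does not follow from the protocol's precision-only sample size calculation

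*SAP*

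**What the plan says.** Protocol 7.2, repeated in 6.2.6, sets out the sample size. "The sample size calculation is based on precision of estimate from the post-operative EQ-5D", with a literature mean of 0.549 and SD of 0.313. The inputs are alpha 0.05, two sides, half-width 0.1 and SD 0.313, giving n=38. It then concludes: "Based on this calculation, a minimum sample size for each device: n = 40 or until sufficient data is collected". Neither section states a power, a null value or a target difference, and the hypothesis in Protocol 5.2 is qualitative.

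SAP 3.1 reports that enrollment was discontinued with 122 patients and that 40 per device was not met. It then claims that a group of 10 "will yield a power of 0.5. Thus, for the purpose of reporting statistically valid outcomes", and on that basis limits summary tables to devices with 10 or more patients. The inputs behind the claim are identified only by the phrase "For the same sample size parameters in the protocol". As to the remaining devices: "Patient data on devices that has less than 10 implanted patients will be provided in the listings". The same section says: "No test of hypothesis will be performed". The primary analysis in SAP 3.1.1 is a "95% confidence interval for the mean change from baseline score in EQ-5D-5L".

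**The concern.** The power figure is the only reason the SAP gives for the threshold and for describing the retained summaries as statistically valid. Power is the probability that a specified test rejects a specified null under a specified alternative. The protocol calculation supplies none of these, and the SAP says that no test will be run.

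The results go to regulatory authorities and notified bodies (SAP 2.1). A reader there could take the sentence to mean that 10 patients per device carry a derived statistical warrant. With 122 patients spread over the 43 devices of SAP Appendix 1, the cut-off may decide which devices appear in the summary tables. The documents do not give patient counts by device, so how many are affected is unknown.

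**Working it through.** **Inputs.** Two-sided alpha 0.05, half-width 0.1, SD 0.313 and n=38 come from Protocol 6.2.6 and 7.2. The figures n=10 and power 0.5 come from SAP 3.1. Where a difference, a second-visit SD or a correlation is used below, it is an assumption and is marked as such.

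**1. The protocol's own figure.** n = (z × SD / half-width)² = (1.96 × 0.313 / 0.1)² = 37.6, rounded up to 38. This reproduces the protocol and shows that the calculation concerns confidence interval width alone.

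**2. Power if the half-width 0.1 is taken as the difference (assumption).** One-sample, two-sided test. At n=10 the standard error is 0.313/√10 = 0.0990, so the standardised difference is 0.1/0.0990 = 1.010. Normal approximation: Φ(1.010 − 1.96) + Φ(−1.010 − 1.96) = 0.171 + 0.0015 = 0.173. The t results are from the noncentral t distribution.

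| n | Power (z) | Power (t) |
|---|---|---|
| 10 | 0.173 | 0.148 |
| 38 | 0.504 | 0.483 |
| 40 | 0.524 | 0.504 |

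On this reading, 0.5 falls at the planned sample size, not at 10. That is by construction: when the difference equals the interval half-width, power is about one half.

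**3. What would give about 0.5 at n=10.**
- A one-sample difference of 1.96 × 0.0990 = 0.194 (z) or 0.217 (t). Neither is in the documents.
- The full interval width, 2 × 0.1 = 0.2, used as the difference (assumption). Power is Φ(0.2/0.0990 − 1.96) = Φ(0.061) = 0.524 (z), or 0.439 (t).
- Change from baseline with a difference of 0.1 and an SD of 0.313 at each visit (assumptions). The SD of change must be 0.1 × √10 / 1.96 = 0.161 (z) or 0.144 (t). Since the SD of change is 0.313 × √(2(1 − ρ)), the correlation is ρ = 1 − SD²/(2 × 0.313²) = 0.87 (z) or 0.89 (t). The documents give no correlation and no SD of change.

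**4. Precision at n=10, on the protocol's own scale.** Half-width for the post-operative mean:
- z: 1.96 × 0.0990 = 0.194
- t on 9 degrees of freedom: 2.262 × 0.0990 = 0.224

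Both are about twice the planned 0.1. For change from baseline, under the same equal-SD assumption, the t half-width at n=10 is 0.317, 0.224, 0.142 and 0.100 at correlations of 0, 0.5, 0.8 and 0.9.

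**5. Scope of the threshold.** Protocol 7.1 says: "All effectiveness and safety analysis will be performed separately for each Wright Medical device included in the study". SAP 6.6 likewise promises an adverse event summary for each device. Neither mentions a minimum number of patients, and SAP 3.1 does not say whether its threshold reaches that table.

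**The case against.** The best defence is that the SAP author may have had a real calculation in mind. SAP 3.1 gives the power to one decimal, and a difference of 0.2 with SD 0.313 gives 0.524 by the normal approximation, which rounds to 0.5. This stands as a possible explanation. It does not support the sentence as written: 0.2 is not a stated parameter, the t calculation gives 0.439, and a null and a test still have to be supplied.

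It does limit what can be claimed. A reader might infer that 0.5 is attainable only at 38 to 40 patients, or that the threshold was never derived from power. The documents support neither. The first holds only if 0.1 is the difference. As to the second, the SAP presents the threshold as following from power; what is missing is the derivation.

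Version control is a further limit. SAP 3.1 cites protocol Version 3, whereas the protocol supplied is Version 2, the version named on the SAP's front page. The SAP repeats 40 per device, but that does not prove that every other input is the same.

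The SAP is also open that 40 per device was not reached and that all analyses are descriptive. It shows a confidence interval only where normality is met, so some devices may have none.

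Finally, a reader might infer that safety data on small devices disappear. They do not: the events remain in Listing 9 and in the by-site summary of SAP 6.6. The threshold in SAP 3.1 can also be read as a general rule that covers the adverse event table, so this is an ambiguity rather than a clear contradiction.

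**Conclusion.** The point holds for the protocol version supplied. A power of 0.5 at n=10 cannot be obtained from the parameters to which SAP 3.1 refers, and power has no role in a plan without tests. Even a correctly derived power of 0.5 would not make a descriptive summary statistically valid.

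The size depends on the reading. With 0.1 as the difference, power is 0.15 to 0.17 rather than 0.5. On the precision scale that the protocol used, the half-width is 0.19 to 0.22 rather than 0.1. That loss of precision concerns the post-operative mean. It should not be carried over to the primary endpoint, whose precision depends on an SD of change that the documents do not give.

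The consequence is confined to the stated justification for the threshold and the scope of the tables. No estimate is affected.

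**What to change.** In SAP 3.1, delete the power sentence and the claim that the outcomes are statistically valid, and put in their place:

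> With the protocol's post-operative SD of 0.313, 10 patients give a 95% CI half-width for the post-operative mean of about 0.19 (z) to 0.22 (t), against the planned 0.1. The protocol specifies no SD for change from baseline. The 10-patient threshold is a pragmatic reporting cut-off.

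If the sponsor holds a derivation of 0.5, SAP 3.1 should instead state its null value, difference, SD and test. The protocol version cited there should be reconciled with the one on the SAP front page.

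As a minor clarification, add one sentence to SAP 3.1 or 6.6 saying whether the threshold applies to the by-device adverse event table. Showing counts and denominators for every device would agree with Protocol 7.1 and SAP 6.6.

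The cost is a few sentences and no new data. If adverse events are shown for all devices, the existing table gains columns.

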### **7.3 Data Analysis**

Improvements in subject quality of life after surgery will be assessed by constructing 95% confidence interval for the mean change from baseline score in EQ-5D-5L and FAMM total and component scores.

|   |  |  |
|---|--|--|
|  | Clinical Investigation Plan
Foot and Ankle Products | CIP- INT19-MDR-001
Version: 2 |
|---|--|--|

Survivorship of a Wright product will be assessed based on adverse event resulting from the presence or performance of the device. The Kaplan Meier survivorship method and life table analysis will be employed. Time to adverse event due to the presence or performance of the implant will be the survivorship endpoint for each Wright device. Also, time to reoperation to exchange or remove any part of the Wright device due to failure of the implant will also determine the Wright product survivorship. Subjects who will not experience these events will be censored at the last follow-up visit. The Kaplan Meier survival curve and the 95% Confidence Interval will be constructed.

Safety endpoints will include all adverse events (AE), serious AE (SAE), unanticipated adverse device effects (UADEs).

All subjects enrolled in the study will be assessed for safety. Adverse events and other safety evaluations will be reported as frequency and rates as appropriate, cumulative over the different follow-up schedules.

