### 6.6. HARMS AND SAFETY

See [Table 5.1](#). The safety of each device will be summarized in the interim and final report. Overall summary of adverse events will be presented for each device. Total frequencies and percentages of adverse events for each Wright device will be summarized for the following factors:

- Procedure-Related Adverse Event / Incident
- Device-Related Adverse Event / Incident
- Device Failure
- Unanticipated Adverse Device Event
- Serious Adverse Event (SAE)
- Hospitalization SAE Outcome
- Treatment Required for the AE

The occurrence and rate of SAE will be further categorized by the outcome of the SAE (i.e., death, hospitalization).

The rates for device failure will be the basis of the survival rates for each device. The above AE factors will also be summarized for each study site.

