## 8. Appendices

### 8.1. Appendix 1. List of Wright medical devices included in the study.

Device	Follow-Up Time Period
611 Nail	1 year
BIOARCH	1 year, 2 year
BIOFOAM Ankle Spacers	1 year
BIOFOAM Wedge System	1 year
CHARLOTTE MUC Screws	1 year
CHARLOTTE Quick Staple	1 year
CHARLOTTE Snap-Off Screws	1 year
CLAW II	1 year
DARCO Headed Screws	1 year
DARCO Headless Screws	1 year
DARCO MFS	1 year
DARCO MRS	1 year
DARCO Plantar Lapidus Plate	1 year
DART-FIRE	1 year
FUSEFORCE	1 year
FUTURA CSI	1 year, 2 year
G-FORCE	1 year, 2 year
GRAVITY SYNCHFIX	1 year, 2 year
HV Screws	1 year
MaxLock Edgelock Plate	1 year
MiniMaxLock ISO Plate	1 year
MICA Screws	1 year
NEXFIX Snap-Off Screws	1 year
Omni Evolution Screws	1 year
ORTHOLOC 2 Ankle Fracture	1 year
ORTHOLOC 2 CROSSCHECK	1 year
ORTHOLOC 2 Small Bones	1 year
ORTHOLOC 3Di Ankle Fusion	1 year
ORTHOLOC 3Di Hallux	1 year
ORTHOLOC 3Di Midfoot/Flatfoot	1 year
ORTHOLOC Forefoot Fracture	1 year
ORTHOLOC Plantar Lapidus	1 year
ORTHOLOC Calc Fracture	1 year
PHALINX	1 year
PITON	1 year
PRO-TOE VO	1 year
SALVATION ExFix	1 year
SALVATION Bolts and Beams	1 year
SALVATION 3Di Plates	1 year
SWANSON Toes	1 year, 2 year, 3 year, 4 year, 5 year, 6 year, 7 year, 8 year, 9 year, 10 year
Telya	1 year
UNIMA EVO and NEUTRA Screws	1 year
VALOR Nail	1 year

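### The SAP's 10-patient cut has no safety exception, so low-volume devices get no device-level adverse event rate or life table, and no all-treated adverse event summary is laid out

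*SAP*

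**What the plan says.** SAP 3.1 records that enrolment stopped early ("At study end date, there were 122 patients enrolled in the study") and that the planned 40 per device was not reached. It then sets a reporting threshold: "descriptive summary statistics will be presented for Wright devices implanted in at least 10 patients enrolled in the study". Below that, "Patient data on devices that has less than 10 implanted patients will be provided in the listings", kept for later reference. The stated reason is that 10 patients, under the protocol's sample-size parameters, "will yield a power of 0.5". Nothing in 3.1 confines the rule to patient-reported outcomes. The same section gives the aim as both performance and safety of each device, and counts a patient under every device received.

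Other passages set no minimum:
- Protocol 7.1 has effectiveness and safety analysed separately for each included device.
- Protocol 7.3: "All subjects enrolled in the study will be assessed for safety", with adverse events given as frequencies and rates.
- SAP 5 defines a treated population of everyone implanted with an Appendix 1 device and applies it to all analyses.
- SAP 6.6: "Overall summary of adverse events will be presented for each device". It also promises the same adverse event factors by study site.

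The SAP's list of tables has three life tables (5.1 to 5.3) and one adverse event table (6.1), all by device. The only adverse event shell, numbered 5.1, has device columns and no total.

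**The concern.** Two instructions in the same plan cannot both be followed. A programmer applying 3.1 would drop devices with fewer than 10 patients from the adverse event table and the life tables. A programmer applying SAP 5 and 6.6 would keep them.

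The threshold also has no safety rationale. It comes from a calculation about the precision of a mean EQ-5D score, and a count such as 1 event in 6 patients needs no minimum sample size to be reported.

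At stake is which safety rates the final report contains. Safety is a stated objective for each device. For a device below the cut, the report would show events line by line without a denominator. The study would also have no planned rate for its treated patients as a whole, which is where its 122 patients carry most information on uncommon events.

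**Working it through.** **1. The basis for the cut.** Inputs from protocol 7.2: alpha 0.05, two-sided, SD 0.313, "Half width (precision) = 0.1".
- Protocol sample size: (1.96 × 0.313 / 0.1)² = 37.6, rounded up to 38. This reproduces the protocol's figure.
- SAP power at n = 10, reading 0.1 as the difference to detect: Φ(0.1 / (0.313/√10) − 1.96) = Φ(1.010 − 1.960) = 0.17. With a t test it is 0.15; one-sided it is 0.26 (z) or 0.24 (t). None is 0.5.
- At n = 38 the same z formula gives 0.504, so power of about 0.5 belongs to 38, not 10. At n = 10 the 95% half-width is 1.96 × 0.313/√10 = 0.194.

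So the stated reason does not reproduce, and it concerns the EQ-5D in any case.

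**2. How many devices fall below 10.** Inputs: 122 patients (SAP 3.1) and 43 devices, counted under "List of Wright medical devices included in the study" in Appendix 1. Devices per patient are not given, so a range is assumed. With m devices per patient, at most floor(122m/10) devices can reach 10.

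| Devices per patient (assumed) | Patient-device pairs | Most devices that can reach 10 | Fewest of 43 below 10 |
|---|---|---|---|
| 1 | 122 | 12 | 31 (72%) |
| 1.5 | 183 | 18 | 25 (58%) |
| 2 | 244 | 24 | 19 (44%) |
| 3 | 366 | 36 | 7 (16%) |

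For 22 of the 43 (a majority) to reach 10 takes 220 pairs, or 220/122 = 1.80 devices per patient, spread almost evenly. These minima include any device with no implants.

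**3. What this says about patients.** Take one device each.
- If 12 devices have 10 patients apiece, 12 × 10 = 120 of 122 patients are in summarised devices and 2 are left out. If those two also received one of the 12, none is left out.
- At the other extreme, 43 devices with 9 patients each could hold 387 patients, more than 122, so it is possible that no device reaches 10 and everyone is left out.

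The documents do not say where between these limits the study lies.

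**4. What a rate would carry.** With zero events, the upper limit of the exact two-sided 95% interval is 1 − 0.025^(1/n):
- n = 9: 33.6%
- n = 10: 30.8%
- n = 122: 3.0%

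The chance of seeing at least one event at an assumed true rate of 2% is 1 − 0.98^n: 16.6% at 9, 18.3% at 10, 91.5% at 122. Nothing changes materially between 9 and 10. The 122 assumes all enrolled patients were implanted, which fits the definition of enrolment in protocol 6.2.3.

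**The case against.** A reader might infer that most devices and their adverse events enter no safety rate at all. The documents do not support that:
- SAP 6.6 promises adverse event factors by study site. Every treated patient belongs to a site, so this could bring low-volume patients into a rate. It lacks a table and a shell, and its denominator is not stated.
- A patient with one low-volume and one higher-volume device is still counted under the latter.
- A majority of devices below 10 is certain only up to about 1.8 devices per patient. A count of devices says nothing definite about events, as step 3 shows.

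Nor is this a failure of detection. Protocol 11.4 has serious events reported to the sponsor within 24 hours, all events reviewed by the sponsor, and serious events summarised annually to ethics committees. The issue is tabulation.

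It can also be argued that the cut was meant for the EQ-5D only, since that is where its parameters come from, and that SAP 3.1 promises column and row totals for qualitative variables. The first is a plausible intention, but 3.1 does not say it. The second does not rescue the adverse event table: the shell shows no total, and summing device columns would count multi-device patients more than once and still omit devices below 10.

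Finally, protocol 7.1 asks for analysis by device, and a pooled rate mixes nails, staples, toe implants and external fixators. That stands: the 3.0% bound describes no single device. It is a reason to present the pooled column as a supplement, not to leave it out. The SAP already pools in its eligibility and protocol deviation shells.

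**Conclusion.** The point holds as a conflict in the plan with a real effect on its output. Read as written, SAP 3.1 removes device-level adverse event rates and life tables for any device with fewer than 10 patients, on a rationale that does not concern safety. Protocol 7.1 and 7.3 and SAP 5 and 6.6 call for the opposite. No all-treated adverse event summary is laid out, and the by-site one exists only as a sentence.

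The size is bounded but not known. The minima of 31 of 43 devices (one per patient) and 19 of 43 (two per patient) rest on assumed devices per patient and include devices that may never have been implanted. The proportion of patients or events missing from the device tables cannot be worked out from the documents.

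**What to change.** - State in SAP 3.1 that the 10-patient rule applies to patient-reported and other effectiveness summaries only. This also brings the smaller devices into the listed life tables.
- For every implanted device, whatever its n, report x/n with an exact 95% CI for adverse events, serious adverse events, device-related adverse events and device failures.
- Add an all-treated column to the adverse event table that counts each patient once, labelled as a supplement to the per-device rates.
- Add a shell for the by-site summary, with its denominator.
- Align the table number: the adverse event table is 5.1 in SAP 6.6 and in the shell, but 6.1 in the list of tables.

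The cost is programming and table space, with more columns if many devices were implanted. No new data are needed, and interval estimates are compatible with the SAP's descriptive-only stance. The downsides are wide intervals for small devices, which is accurate information, and a pooled rate over unlike devices, which needs a footnote saying so.
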